5 LIST OF ABBREVIATIONS AND TERMS

AE(s)	Adverse Event(s)
ANCOVA	Analysis of Covariance
ATRA	All Trans Retinoic Acids: Tretinoin
BPO	Benzoyl Peroxide
°C / °F	Degrees Centigrade / Degrees Fahrenheit
CFR	Code of Federal Regulations
ClinRo	Clinician Reported Outcome
CRA	Clinical Research Associate
CRO	Contract Research Organization
E-ATRA	Encapsulated All Trans Retinoic Acid: Encapsulated tretinoin
E-BPO	Encapsulated Benzoyl Peroxide
eCRF	Electronic Case Report Form
FDA	Food and Drug Administration
G	Grams
cGCP	current Good Clinical Practice
H	Hour(s)
hCG	Human Chorionic Gonadotropin
HIPAA	Health Insurance Portability and Accountability Act
HRQoL	Health related Quality of Life
IB	Investigator's Brochure
ICF	Informed Consent Form
ICH	International Conference on Harmonization
IGA	Investigator's Global Assessment
IND	Investigational New Drug
IRAE	Immediately Reportable Adverse Event
IRB	Institutional Review Board
ITT	Intent To Treat
IWRS	Interactive Web Response System
MCMC	Markov Chain Monte Carlo
MedDRA	Medical Dictionary for Regulatory Activities
Min	Minutes
Mg	Milligram
NRS	Numeric Rating Scale
OTC	Over The Counter
PGI-C	Patient Global Impression of Change
PGI-S	Patient Global Impression of Symptom Severity
PGI-SE	Patient Global Impression of treatment Side-Effects
PGI-TS	Patient Global Impression of Treatment Satisfaction
PI	Principal Investigator
PRE-FACE	Patient-Reported Evaluation of Facial Acne
PRO	Patient Reported Outcome
PP	Per Protocol
Qd	Once a Day
QoL	Quality of Life
SAE	Serious Adverse Event
SAP	Statistical Analysis Plan
Sub-I	Sub-Investigator
TEAE	Treatment-Emergent Adverse Event

VRS

Verbal rating scale

6 INTRODUCTION AND BACKGROUND

Acne vulgaris is a common condition of the pilosebaceous units of the skin (hair follicles and oil glands). Acne is the most common skin disorder in the United States, affecting 40-50 million Americans. Acne usually begins in puberty, but the condition is not restricted to any age group.

Approximately 85% of people between the ages of 12 and 24 experience at least minor, most often on the face, chest, and back ([Bhate, 2013](#)). Acne is caused by four major factors:

1. Production of oil by enlarged oil glands in the skin.
2. Blockage of the hair follicles that release oil.
3. Growth of bacteria, called *Propionibacterium acnes*, within the hair follicles.
4. Inflammatory/immune response to *P. acnes*

The pathophysiologic features of acne suggest that combination therapy should be utilized as early as possible to simultaneously attack the multiple pathogenic factors of the condition ([Gollnick 2003](#)). Antimicrobials have been a mainstay of acne treatment for many years, having multiple mechanisms of action. The most important may be the ability of antibiotics to decrease the number of *P. acnes* in and around the follicle. They have a bacteriostatic effect on *P. acnes*, which prevents the bacteria from producing pro-inflammatory molecules ([Leyden 2001](#)).

In clinical practice, it is common for physicians to prescribe multiple topical products for acne. Topical products are applied one or two times a day by the Patient. However, many of these compounds are irritating with resultant development of facial erythema and discontinuation of the products or noncompliance with therapy. Benzoyl peroxide (BPO) and tretinoin (ATRA) are two active ingredients with different pharmacological actions that are commonly used for the treatment of acne.

Topical retinoids are keratinization inhibitors. They work by decreasing the cohesiveness of follicular epithelial cells. This, results in an inhibition in the formation of microcomedones, preventing the formation of mature comedones and inflammatory lesions ([Gollnick 2003](#)). Use of retinoids promotes the normal desquamation of follicular epithelium. The action of the retinoid may enhance the penetration of other topical compounds used to treat acne.

Benzoyl peroxide (BPO) is a commonly used topical antibacterial agent for acne available either by prescription or over the counter (OTC). BPO has been found to be lethal to *P. acnes* as well as other bacteria that may reside on the skin. So far there has been no indication of any bacteria developing a resistance to BPO. It has also been demonstrated that BPO has keratolytic activity contributing to its efficacy in treating comedonal acne ([Tanghetti 2008](#)). BPO reduces the cohesiveness of the cells of the stratum corneum, thus improving topical drug delivery through the epidermal barrier.

Silica microcapsule systems have been developed to overcome many of the limitations

(such as degradation and irritation) of standard pharmaceutical formulations involving multiple active ingredients. The encapsulation of active ingredients in silica microcapsules serves to protect components in the formulation from interacting with one another and, as a consequence, increases overall formulation stability. Silica is chemically inert, photochemically and physically stable, and safe for topical use. Sol-Gel's silica encapsulated products meet the criteria for categorical exclusion defined in 21 CFR 25.31(e), and that to the knowledge of Sol-Gel, no extraordinary circumstances exist as defined in 21 CFR 25.21. Thus, no environmental assessment is required according to 21 CFR 25.20(l). For the case of E-BPO/E-ATRA, microencapsulation of both BPO and tretinoin protects the tretinoin from oxidative decomposition by BPO, thereby enhancing the stability for this novel combination product and ensuring a suitable clinical and commercial shelf life. The encapsulation may also contribute to decreased skin irritation as evidenced in the 14-day minipig irritation study referenced in the nonclinical section of the Investigator's Brochure.

Combination topical therapy is the recommended standard of care for the management of Patients with acne ([Gollnick 2003](#)). Combination therapy targets multiple pathogenic factors: abnormal follicular keratinization, P. acnes proliferation and inflammation. Combining the separate product applications into a single delivery system would provide the Patient with the convenience of a single product, thus improving Patient adherence and improving treatment outcomes.

[REDACTED]

[REDACTED]

[REDACTED]

[REDACTED]

7 OBJECTIVES

The primary objectives of this pivotal study are:

1. To assess the efficacy of S6G5T-3 compared to its Vehicle when applied once daily for 12 weeks in Patients with acne vulgaris.
2. To assess the safety of S6G5T-3 when applied once daily for 12 weeks in Patients with acne vulgaris.

The co-primary efficacy endpoints are to be evaluated using the following parameters:

- Proportion of Patients with an assessment of clear or almost clear and with at least a 2-grade improvement in IGA from baseline at Week 12.
- Absolute change from Baseline in lesion count on the face at Week 12 (separately for inflammatory and non-inflammatory lesions).

The secondary objective of this pivotal study is:

To demonstrate statistical superiority in efficacy of Products S6G5T-3 as compared to the vehicle regarding percent change from baseline.

The secondary efficacy endpoints will be the following:

- Percent change from Baseline, in non-inflammatory lesion count at Week 12.
- Percent change from Baseline, in inflammatory lesion count at Week 12.
- Proportion of Patients in the E-BPO/E-ATRA cream arm compared to vehicle control achieving at least a 4-point reduction on Item 1 (pimples) of the PRE-FACE from Baseline to Week 12.
- Proportion of Patients in the E-BPO/E-ATRA Cream arm compared to vehicle control achieving at least a 4-point reduction on Item 5 (embarrassment) of the PRE-FACE from Baseline to Week 12.
- Absolute change from Baseline, in non-inflammatory lesion count at Week 8
- Absolute change from Baseline, in inflammatory lesion count at Week 8.
- Absolute change from Baseline, in non-inflammatory lesion count at Week 4.
- Absolute change from Baseline, in inflammatory lesion count at Week 4.

The supportive objective of this pivotal study is:

To determine the time required to observe improvement in the efficacy parameters associated with clearance of acne for Products S6G5T-3 compared to vehicle.

Supportive efficacy endpoints include the following:

- Proportion of Patients with an assessment of clear or almost clear and with at least a 2-grade improvement in IGA from Baseline, at Weeks 2, 4 and 8.
- Absolute change from Baseline in inflammatory and non-inflammatory lesion counts from Baseline to weeks 2, 4 and 8.
- PRE-FACE ASD: Mean absolute change in PRE-FACE ASD scores from Baseline to Weeks 2, 4, and 8.
- PRE-FACE AID: Mean absolute change in PRE-FACE AID scores from Baseline to Weeks 2, 4, and 8.
- Proportion of Patients in treatment relative to control who report at least “minimally improved” as measured by the PGI-C at Week 12.
- Patient Global Impress of Symptom Severity (PGI-S) at Week 12.

- Patient Global Impression of Treatment Satisfaction (PGI-TS) at Week 12.

The safety objectives of this pivotal study are:

To determine the nature, severity and frequency of the AEs rate and the local cutaneous reaction and tolerability of Products S6G5T-3 compared to the vehicle.

The safety endpoints to be assessed include the following:

- The frequency of both local and systemic AEs
- Investigator Cutaneous Reaction (erythema, dryness, pigmentation and scaling) and Local Tolerability Assessment (itching burning and stinging) at Baseline and at all study visits.

8 ETHICS

This study will be conducted in compliance with FDA regulations, the ethical principles of the Declaration of Helsinki, and the current ICH- Good Clinical Practice (cGCP) guidelines. The Investigator and all study staff will conduct the study in compliance with this protocol.

The protocol, informed consent documents, any information provided to study Patients, recruitment advertisements and any amendments to these items will have Institutional Review Board (IRB) approval prior to their use in the study. Voluntary informed consent will be given by every Patient prior to the initiation of any study related procedures. The rights, safety and well-being of the study Patients are the most important considerations and prevail over the interests of science and society.

All personnel involved in the conduct of this study must be qualified by education, training and experience to perform their assigned responsibilities.

9 INSTITUTIONAL REVIEW BOARD (IRB) AND INFORMED CONSENT

Before study initiation, this protocol, the investigational brochure for Encapsulated Benzoyl Peroxide 3%/Encapsulated All-Trans-Retinoic Acids 0.1% Cream (E-BPO/E-ATRA 3%/0.1%) in the treatment of acne vulgaris, the ICF, and any other written information given to Patients, and any advertisement for Patient recruitment must have IRB approval. The Investigator will submit documentation of the IRB approval to the Sponsor, Sol-Gel Technologies Ltd., or their Contract Research Organization (CRO) designee.

The IRB-approved ICF must include all elements required by the Food and Drug Administration (FDA), state, and local regulations, and may include appropriate additional elements.

The Investigator/designee will explain the study to each potential Patient and the Patient must indicate voluntary consent by signing and dating the approved ICF. The consent process will be conducted prior to the start of any study-related procedures including a washout period. The Investigator must provide the Patient with a copy of the ICF, in a language the Patient understands.

The Investigator will maintain documentation that informed consent was obtained prior to the initiation of any study-related procedures.

10 OVERALL STUDY DESIGN

This study will be a randomized, double-blind, multicenter, parallel group, active- and vehicle-controlled pivotal study to assess efficacy, and safety of Products S6G5T-3 and its vehicle for the treatment of acne vulgaris for 12 weeks. Approximately 420 Patients with moderate to severe acne vulgaris (rated 3 or 4 on the 5-point IGA) will be enrolled at up to 25 sites. Patients in this randomized, double-blind, vehicle-controlled, parallel-group multi-center study will be randomly assigned in a 2:1 ratio to Encapsulated Benzoyl Peroxide 3%/Encapsulated All-Trans-Retinoic Acids 0.1% (E-BPO/E-ATRA) Cream or Vehicle Cream respectively. Patients with severe acne vulgaris who are appropriate for systemic treatment need to be counseled regarding their treatment options by the Principal Investigator (PI).

The overall schedule of study visits includes:

- Visit 1/Screening
- Visit 2/Baseline, Day 1
- Visit 3/Week 2, Day 15 (\pm 3 Days)
- Visit 4/Week 4, Day 29 (\pm 3 Days)
- Visit 5/Week 8, Day 57 (\pm 3 Days)
- Visit 6/Week 12, Day 85 (\pm 4 Days) / End of Study or Early Termination

Treatment efficacy will be evaluated using both clinician reported outcome (ClinRO) and Patient-reported outcome (PRO) questionnaires. Clinician reported efficacy assessments will include facial inflammatory and non-inflammatory lesion counts and an IGA which asks assessors to rate Patient's acne from 0 (Clear) to 4 (Severe). Patient reported efficacy assessments include the Patient-Reported Evaluation of Facial Acne (PRE-FACE), the Patient Global Impression of Symptom Severity (PGI-S), the Patient Global Impression of Change (PGI-C), and the Patient Global Impression of Treatments Satisfaction (PGI-TS).

Safety will be assessed at all visits and will include monitoring local and systemic AEs; the Investigator Cutaneous Safety Assessment rating of pigmentation, erythema, dryness and scaling on a scale ranging from 0 (None) to 3 (Severe) and the Patient assessment of Local Tolerability Assessment rating itching, burning and stinging on a scale ranging from 0 (None) to 3 (Severe). A Patient Global Impression of Treatment Side Effects (PGI-SE) will also be administered as part of the study design.

Clinician reported outcomes will be collected at study Visit 1, 2, 3, 4, 5 and 6. Patient-reported outcomes will be collected at study visit 2, 3, 4, 5, and 6 (with the exception of the PGI-C, PGI-TS and PGI-SE) which are not collected at Visit 1 or Visit 2). AEs and concomitant medications will be assessed throughout the treatment period. A urine pregnancy test is required at Visit 1, 2, 3, 4, 5 and 6 for all females of child-bearing potential and premenarchal.

11 STUDY POPULATION

11.1 Randomization and Blinding

It is planned that approximately 420 Patients, who meet the inclusion/exclusion criteria, will be enrolled in this study at up to 25 U.S. study sites. Patients will be at least 9 years of age and older, of either gender.

The study products will be administered in a double-blinded fashion (i.e., the treatment assignment will not be known to the Patient or to study personnel including Sol-Gel and its representatives). Patients will be instructed not to discuss the study product with the study personnel. Patients will be randomly assigned, in a 2:1 ratio, as follows:

- E-BPO/E-ATRA 3%/0.1% Cream (Product S6G5T-3) (280 Patients)
- Vehicle Cream (Product S6G5T-8) (140 Patients)

Each Patient who signs an informed consent, meets inclusion/exclusion criteria, and successfully completes the screening procedures will be enrolled in the study. The Patient randomization schedule will be a permuted block design stratified by investigational site. Blocks will be composed of 3 treatment assignments in a ratio of 2:1 Product S6G5T-3 and vehicle respectively. Complete blocks from the randomization schedule will be allocated to investigational sites as they randomize Patients to maintain the randomization ratio of 2:1 Product S6G5T-3 and vehicle respectively.

Additionally, the staff involved in data management and statistical evaluation will remain blinded until identification of the per protocol population is finished and the database is locked.

The randomization schedule and treatment code will not be revealed to the Patients, study personnel, Sol-Gel or its representatives until after the database lock, except to the Medical Monitor or PI in the case of an emergency unblinding. Access to the randomization list will be maintained by and limited to the unblinded Biostatistician and the designated personnel directly responsible for labeling of study materials. The Medical Monitor will not have access to the randomization list, but may determine that unblinding of one or all Patients may be necessary in the case that the safety of study Patient(s) is at risk. In an emergency, the study blind may be broken only if:

- In the opinion of the Medical Monitor and/or the PI, it is in the Patient's best interest to do so.
- Knowledge of the treatment will alter the clinical management of the Patient.

In the case of an emergency that requires unblinding, the Investigator can request to unblind the Patient without prior contact with the Medical Monitor although follow-up between the Investigator and Medical Monitor must occur so that all parties are aware of the unblinding. Although it is recommended that the Investigator contact the Medical Monitor prior to unblinding any Patient, in instances where this is not feasible or advisable, the PI may directly access the Patient's treatment assignment. In all situations, the Interactive Web Response System (IWRS), will be used to obtain treatment assignment information, with limited access to only the above-designated individuals; and any unblinding will be documented in the source records accordingly.

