Pump usage will be demonstrated by the site personnel on a sample pump at the clinic to help assure the Patient understands the procedure. The Patient will be provided a set of instructions ([Appendix 1](#)) that includes study reminders and restrictions as described in this protocol. Patients will be instructed to bring the study product to every visit, excluding to Visit3/ Week 2. Patients should be instructed to store the study product at room temperature, not in the refrigerator or freezer and informed that the test article may bleach colored fabric like clothing and bed sheets.

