18.4 Required Study Documents

The Investigator must provide the following documents to Sponsor or CRO designee before any Patients are enrolled and/or study product may be shipped to the study site:

- The signed 'Investigator Protocol Acknowledgment' page from the Sponsor and IRB approved protocol.
- Documentation of IRB approval of the protocol, ICF, any other written information provided to Patients and any recruitment advertisements.
- A copy of the IRB approved ICF.
- A current IRB assurance number and/or a membership roster.
- A completed, signed and dated Form FDA 1572.
- The appropriate financial disclosure documentation.
- A current signed and dated curriculum vitae and a copy of the current medical license for the Investigator and Sub-Investigators listed on the Form FDA 1572.
- The signed agreement between the Investigator and Sponsor, or designee, and related financial information for the study.

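### A single block size of 3 within site, printed in the protocol that sites hold, allows avoidable prediction within blocks: at most 4/9 of assignments, and only if earlier ones are known

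*Protocol*

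**What the plan says.** Protocol 11.1 describes a "permuted block design stratified by investigational site" and adds: "Blocks will be composed of 3 treatment assignments in a ratio of 2:1". It continues: "Complete blocks from the randomization schedule will be allocated to investigational sites" as those sites randomize. Protocol 12.4 and SAP 6.1.2 repeat the scheme. None of the three gives a second block size or says that the size varies. Protocol 16.3 also has supplies shipped in threes to hold the 2:1 ratio.

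Sites hold this text. Protocol 18.4 requires from each investigator, before enrolment or drug shipment, "The signed 'Investigator Protocol Acknowledgment' page from the Sponsor and IRB approved protocol". Nothing in either document says that the block size is withheld from sites.

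The stated protections are double-blinding, identical-looking cartons (16.3), assignment through the IWRS with scrambled kit numbers (12.4), a restricted randomization list, and an instruction to patients not to discuss the product with study staff (both 11.1). Under 11.1 the investigator can obtain a patient's assignment in an emergency, and the unblinding must be documented.

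**The concern.** In a 2:1 block of 3 the last assignment always follows from the first two, and a vehicle patient in first place settles the other two as active. Because whole blocks go to one site, staff who know the size can follow block boundaries in their own randomization order.

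Two of the three co-primary tests are lesion counts made by site evaluators, and the third is the investigator's IGA. The IGA and the counts also decide eligibility. Knowing the next assignment could influence who is enrolled. Knowing a block-mate's assignment could influence how a patient already enrolled is scored.

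The documents name several ways an earlier assignment might come to light: emergency unblinding (11.1); scored local reactions (14.1, 14.2); two excipients present only in the vehicle (16.2; whether they change its appearance is not stated); and the warning to patients that "the test article may bleach colored fabric like clothing and bed sheets" (16.5).

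**Working it through.** **Inputs.** Block size 3 at 2:1 within site, with complete blocks to sites (Protocol 11.1, 12.4; SAP 6.1.2). Planned total 420, split 280 and 140 (Protocol 11.1). Up to 25 sites in Protocol 11.1 and up to 31 in SAP 6.1.2. The documents give no predictability figure.

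**The plan's allocation reproduces.** 420/3 = 140 blocks; 140 × 2 = 280 active; 140 × 1 = 140 vehicle.

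**Certain share with earlier assignments known.** The three equally likely orders are AAV, AVA and VAA (A active, V vehicle).

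| Position | Certain when | Probability certain | Best-guess accuracy |
|---|---|---|---|
| 1st | never | 0 | 2/3 |
| 2nd | 1st was V | 1/3 | (2/3)(1/2) + (1/3)(1) = 2/3 |
| 3rd | always | 1 | 1 |

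- Certain share = (0 + 1/3 + 1)/3 = 4/9 = 44.4%, or 420 × 4/9 ≈ 187 assignments.
- Best-guess accuracy = (2/3 + 2/3 + 1)/3 = 7/9 = 77.8%, against 66.7% from always guessing active.

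Incomplete last blocks lower the share slightly. With 25 sites each ending on one extra patient it is (395 × 4/9)/420 = 41.8%. With two extra it is (370 × 4/9 + 25 × 1/3)/420 = 41.1%. With 31 sites the same sums give 41.2% and 40.3%.

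**Earlier assignments inferred with error.** Suppose each earlier assignment is identified correctly with probability r, with the same error rate for both arms (an assumption). At the 2nd position the best guess stays active whatever is inferred. At the 3rd, guessing vehicle pays only when both earlier patients look active and r² > 2r(1 − r), that is r > 2/3. Overall accuracy is 2/3 for r up to 2/3, and 2/3 + (3r² − 2r)/9 above it.

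| r | Best-guess accuracy |
|---|---|
| 0.60 | 66.7% |
| 0.70 | 67.4% |
| 0.80 | 70.2% |
| 0.90 | 73.7% |
| 1.00 | 77.8% |

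**One emergency unblinding.** If the patient is on vehicle (probability 1/3), both block-mates are active for certain. If the patient is active, one vehicle remains among two block-mates, so each is active with probability 1/2.

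**Varying block sizes.** This was simulated over the first 12 patients at a site. Sizes were equally likely; the observer knew the candidate sizes and all earlier assignments but not the block boundaries.

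| Scheme | Certain share | Best-guess accuracy |
|---|---|---|
| Fixed 3 | 44% | 77.8% |
| 3 and 6 | about 9% | about 75% |
| 3, 6 and 9 | about 3% | about 73% |

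For comparison, a larger fixed size that sites know still leaves 13/45 = 28.9% certain for size 6 and 3/14 = 21.4% for size 9.

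**The case against.** The strongest reply is that the 44% needs assignments to be known, whereas site staff would at best infer them. That stands. A reader might infer that 44% of this trial's assignments will be predictable, or that the leak shrinks in proportion to guessing accuracy. Neither follows: under the error model above there is no gain at all until r exceeds 2/3.

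Nor do the documents show that inference would be good. SAP Section 4 reports that in Phase 2 the investigator-rated skin and tolerability complaints tended to stay as at baseline. Only self-assessed scaling, burning and stinging were slightly more frequent on S6G5T-3. Cues are not excluded, since application-site dryness, exfoliation and pain were among the common adverse events, but no accuracy of guessing is supported.

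A reader might also infer that block size compromises blinding of the co-primary outcomes through local reactions or bleaching. Those signs would reveal the patient who shows them under any block size; the block adds only inference about block-mates. Nor do the documents require the tolerability rater to be the IGA rater. Sections 14.1 and 14.2 refer only to the evaluator, and 12.17 asks for the same evaluator at Baseline and Week 12.

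It could be said that cues come too late to affect enrolment. That is only partly so. With even accrual over about 9 months (roughly 274 days) at 25 sites, a site takes 420/25 = 16.8 patients, one every 16 days or so. The third patient in a block then enters about 32 days after the first, by which time the Week 2 visit has normally taken place. Even accrual is an assumption.

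Finally, the gain in best-guess accuracy from varying the sizes is modest, about 3 to 5 percentage points at worst-case knowledge. That also stands; the main gain is that certainty largely disappears.

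**Conclusion.** The point holds as a design weakness, not as an error or contradiction. One disclosed block size of 3 within site makes up to 4/9 of assignments certain and lifts best-guess accuracy from 66.7% to 77.8%. This requires complete blocks, traceable block boundaries and known earlier assignments. With 60% to 80% correct inference (assumed), accuracy is 66.7% to 70.2%, so the realistic effect is small. What is at stake is foreknowledge at enrolment and inference from block-mates; disclosure through a patient's own reactions is a separate matter. The priority is minor to moderate. It is worth acting on because the trial is pivotal, the co-primary outcomes depend on site judgement and the remedy is cheap.

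**What to change.** Generate the IWRS list with block sizes varying at random within site, either 3 and 6 or 3, 6 and 9, keeping 2:1 within each block. If randomization has begun, do this for the unused blocks, since blocks are released to sites as they randomize. Take the block size out of Protocol 11.1 and 12.4 and the shipping text in 16.3, and out of SAP 6.1.2 if sites can see it. Hold it in a restricted randomization document. Kits can still be packed and shipped in threes without the site text saying so.

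The sample size, analysis model and kit packaging do not change. The costs are a regenerated list, a text amendment, and slightly larger possible arm imbalance in a site's last incomplete block.
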